7.8.7 Intraocular Pressure

Intraocular pressure will be measured in mmHg at Visit 1 Screening, Visit 3 Day 1, Visit 4 Day 7+/-2 and Visit 5 Day 14+/-2.

Intraocular pressure and its change from baseline will be summarized descriptively by eye (study or non-study) visit and treatment group.

All results will be listed.

7.8.8 Dilated Fundus Examination

A dilated fundus examination will be administered at Visit 1 Screening and Visit 5 Day 14+/-2. In it, appropriate eye drops will be used to dilate or enlarge the pupil in order to obtain better view of the fundus of the eye. Once the pupil is dilated, an ophthalmoscope or indirect lens will be used to view the eye structures:

1. Optic Nerve Head: classified as Normal or Glaucomatous; horizontal and vertical cup/disc ratio measured.
2. Lens: examined for opacities and other challenges; classified as Normal, Abnormal Not Clinically Significant or Abnormal Clinically Significant
3. Vitreous: classified as Normal, Abnormal Not Clinically Significant or Abnormal Clinically Significant
4. Retina: classified as Normal, Abnormal Not Clinically Significant or Abnormal Clinically Significant

Number and percentage of subjects with each kind of assessment will be tabulated by eye (study or non-study), fundus structure, visit and treatment group. Horizontal and vertical cup/disc ratios will be summarized descriptively by eye (study or non-study), visit and treatment group.

7.8.9 Exposure to Product

The subjects will be instructed to use the diary to document all doses taken. Additionally, the dose taken one day prior to the surgery will be recorded on the eCRF.

Compliance with scheduled application of IP will be determined from the subject's diary as $[\text{Actual number of doses}] / [\text{Planned number of doses}] * 100\%$, where

- Actual number of doses will counted from the subject diary and relevant eCRF pages;
- Planned number of doses is 17 (i.e. Days -1 through Day 14 with two doses taken on Day 0).

Number of missed doses will be calculated as the number of planned dosing time-points when the study drug was not taken during the 16 days starting with the date of the first dose. There is one dosing time-point per each day, except the day of Visit 2 Day 0, when there are two planned time-points, before the surgery and after the surgery.

Subjects who missed dosing for more than 3 consecutive days will be considered non-compliant and will be excluded from the PP population.

Subjects can be additionally excluded from the PP population due to non-compliance, if the Investigator's and Sponsor's review of their dosing times suggests a clinically meaningful departure from the once-daily dosing pattern.

Subjects will be considered compliant if they administer at least 14 doses and not more than 20 doses, with no more than 3 consecutive missed dosing days. The compliance will be analyzed using the descriptive statistics by treatment group. The proportion of compliant vs. non-compliant subjects will be tabulated for each treatment.

Duration of exposure will be calculated as Date of last use of the study drug – Date of first use of the study drug + 1. Duration of exposure will be summarized descriptively by treatment group.

Compliance, number of doses and duration of exposure will be summarized for the Safety and mITT populations.

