#### TEST OF EQUIVALENCE:

• The PP population includes all randomized subjects who meet all inclusion and exclusion criteria,

• The safety population includes all randomized subjects who receive study drug.

Subjects who discontinue because of lack of treatment effect after completing two days of treatment should be analyzed in the mITT and PP populations as a treatment failure. Subjects discontinued for other reasons, including drug-related adverse events, should be excluded from the PP population, but included in the mITT population using Last Observation Carried Forward (LOCF).

The recommended primary endpoint is the proportion of subjects with cure at Visit 5 (end of the study on day  $14 \pm 2$  days) defined as a score of 0 for aqueous cells, a score of 0 for aqueous flare and a score of no more than 3 for pain.

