#### 8.5 Visit 5: End of Study Visit/Early Discontinuation Visit (Day 14 ± 2 Days)

- 1. Review of subject diary card to assess if any adverse events, changes in concomitant medication & compliance to study drug.
- 2 Retrieve the subject diary pages for completed visit and keep in the source file of the patient
- 3. Collect the study medication container from the subject.
- 4. Physical Examination and Vital signs. At a minimum, the physical examination will include the following: assessment of general appearance, skin, HEENT, heart, lungs, musculoskeletal system, lymph nodes, neurological systems, gastrointestinal system, genitourinary system and extremities.
- 5. Assessment of ocular pain
- 6. Visual acuity assessment
- 7. Slit Lamp Examination
- 8. Assessment of Intraocular pressure
- 9. Fundus Examination
- 10. Urine Pregnancy Test (for females of child bearing potential)
- 11. The laboratory evaluation for routine hematology, biochemistry and urine analysis.
- 12. A standard of care treatment may be advised at the Investigator's discretion.

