#### **11.7 Assessment of Compliance**

A subject diary will be provided to all subjects where it is required to document the date and time of administration of the study drug. In the subject diary, subjects will also note any adverse event observed and any concomitant medication taken or changes.

Compliance will be determined from the subject diary, which the subject will be trained and instructed to use to record all doses, as well as all missed doses. The number of missed and additional doses will be captured on the compliance page of the CRF.

Subject who misses 3 consecutive doses of study medication will be considered noncompliant and discontinued from the study. The used kits of study medication will be returned to the study site at appropriate visits or early termination or as applicable.

Subject who will take less than 14 doses of total study drug during the study will be considered non-compliant and discontinued from the study. Subjects who will take more than 20 doses of the study drug are also considered as non-compliant and discontinued from the study.

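### SAP 7.8.9 shows no exception for lack-of-effect discontinuations, so its compliance rules can remove from PP the treatment failures that the protocol Synopsis keeps there

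*SAP*

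**What the plan says.** **SAP 7.8.9 (Exposure to Product)**
- Denominator for percent compliance: "Planned number of doses is 17 (i.e. Days -1 through Day 14 with two doses taken on Day 0".
- A missed dose is a planned time-point "when the study drug was not taken during the 16 days starting with the date of the first dose". The text does not end this window at Visit 5 or at discontinuation.
- A subject is "compliant if they administer at least 14 doses and not more than 20 doses, with no more than 3 consecutive missed dosing days".
- Consequence for the analysis set: "Subjects who missed dosing for more than 3 consecutive days will be considered non-compliant and will be excluded from the PP population".

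**Protocol**
- Synopsis, Test of Equivalence: "Subjects who discontinue because of lack of treatment effect after completing two days of treatment should be analyzed in the mITT and PP populations", counted as treatment failures.
- Section 9.0: subjects who worsen and need alternate or supplemental therapy are discontinued and left out of the PP analysis.
- Section 11.7: non-compliance applies to a "Subject who will take less than 14 doses of total study drug during the study", and also to a subject who misses 3 doses in a row. Both are to be discontinued.
- Section 8.5: Visit 5 falls on Day 14 ± 2, and one of its tasks is "Collect the study medication container from the subject".

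SAP 6.3 gives the PP definition, but most of its criteria are redacted. SAP 7.7.1.1 and Protocol 12.9 test equivalence in PP only.

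**The concern.** A subject who stops early for lack of effect has few doses and a run of undosed days up to Day 14, because treatment ended. The Synopsis treats that subject as an informative failure who belongs in the equivalence analysis. SAP 7.8.9, read literally, treats the same subject as a poor complier and takes the failure out of the PP denominator.

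Equivalence rests on the PP difference in cure proportions, so removing failures raises the cure proportion in each arm by an amount that depends on how many early failures that arm has. If the arm with the lower cure rate also has more early failures, the difference shrinks towards equivalence. SAP 7.5 adds to the risk, because deviations derived by program take precedence over those reported by sites. A literal program could therefore apply the exclusion without anyone deciding on it.

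A smaller, separate matter is that the fixed 17 doses and 16 days do not follow the Visit 5 window. The reported adherence figures therefore depend partly on the visit date.

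**Working it through.** **Inputs.** One dose a day from Day -1, with two on Day 0 (SAP 7.8.9). Visit 4 on Days 5 to 9 and Visit 5 on Days 12 to 16 (SAP 3.1). The dose on the day of Visit 4 or 5 is taken before the visit (Protocol Appendix II, item 13). No dosing after Visit 5, since the bottle is collected.

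**1. The plan's own figure.** Days -1 to 14 are 16 days. One extra dose on Day 0 gives 16 + 1 = 17, which reproduces exactly.

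**2. Subjects who take every dose up to last dosing day d (d from 1 to 14).** Doses = d + 3. Percent compliance = (d + 3)/17. Trailing undosed days within the fixed window = 14 − d.

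| d | Doses | % of 17 | Trailing undosed days | At least 14 doses? | No more than 3 consecutive days? |
|---|---|---|---|---|---|
| 2 | 5 | 29.4 | 12 | no | no |
| 5 | 8 | 47.1 | 9 | no | no |
| 7 | 10 | 58.8 | 7 | no | no |
| 9 | 12 | 70.6 | 5 | no | no |
| 10 | 13 | 76.5 | 4 | no | no |
| 11 | 14 | 82.4 | 3 | yes | yes |
| 12 | 15 | 88.2 | 2 | yes | yes |
| 13 | 16 | 94.1 | 1 | yes | yes |
| 14 | 17 | 100.0 | 0 | yes | yes |

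Both rules switch between Day 10 and Day 11. A failure stopped at Visit 4 (Days 5 to 9) has 8 to 12 doses and 9 to 5 trailing days, so it always falls on the non-compliant side. With the protocol's threshold of 3 consecutive misses in place of the SAP's more than 3, Day 11 would fail as well.

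**3. Would a per-subject denominator and window be enough?** No. For a last dose on Day 5, planned doses become 8, compliance is 8/8 = 100% and missed doses are 0. But 8 is still below 14, so the non-compliant label stays. The same holds for every last dosing day up to Day 10.

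**4. Fully adherent subjects and the Visit 5 date.** Day 12 gives 15/17 = 88.2% with 2 missed doses, and Day 13 gives 16/17 = 94.1% with 1 missed. Both are compliant.

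**5. Subjects who do miss doses.** Misses tolerated by the 14-dose floor = doses possible − 14. Day 12: 15 − 14 = 1. Day 14: 17 − 14 = 3. Day 16: 3 if dosing ends on Day 14, or 19 − 14 = 5 if it runs to the visit.

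**6. What removing failures could do (assumed figures; the documents give none).** Take true cure of 60% on test and 70% on reference, a difference of −10.0 points. Remove 5% of reference subjects, all failures: 0.70/0.95 = 73.7%.
- Remove 5% of test: 0.60/0.95 = 63.2%, difference −10.5.
- Remove 10% of test: 0.60/0.90 = 66.7%, difference −7.0.
- Remove 15% of test: 0.60/0.85 = 70.6%, difference −3.1.

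Equal removal barely moves the estimate. The largest imbalance shown moves it by 10.0 − 3.1 = 6.9 points, against a margin of 20.

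**The case against.** Much of the case on the other side stands.

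- A reader might infer that the fixed 17 decides who is compliant or who is in PP. It does not. It feeds only the percentage, which is summarised for the Safety and mITT populations. The label comes from the 14-to-20 range and the consecutive-days rule. A fixed planned regimen is also a legitimate exposure measure.
- A reader might infer that fully adherent subjects lose PP status through an early Visit 5. They do not: 15 or 16 doses are within range. The visit date matters only for a subject who also misses doses, and no visible sentence ties the 14-dose floor itself to PP exclusion.
- A reader might take it as settled that the SAP removes these failures from PP. It is not. The redacted criteria in SAP 6.3 may keep them, SAP 8 declares no change from the protocol's analyses, and the consecutive-days sentence names no window. Counting days after withdrawal as missed is one reading, though the fixed 16-day window next to it invites that reading. If 6.3 does contain an exception, the unconditional sentence in 7.8.9 conflicts with it.
- Figures of 18 or 19 doses, 112% and 5 tolerated misses hold only if dosing runs past Day 14. The stated schedule ends 14 days after surgery. Appendix II, with its dose before Visit 5, points the other way for a late visit.
- The protocol does not speak with one voice. Section 9.0 excludes from PP a group that overlaps with the one the Synopsis keeps in.
- A reader might say that the 14-dose rule cannot work because an adherent subject has only 8 to 12 doses at Visit 4. Section 11.7 refers to the total over the study, so this is at most loose wording about discontinuation.

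**Conclusion.** The point holds as a conflict between rules in the visible text. The exclusion sentence in SAP 7.8.9 is unconditional and the protocol Synopsis keeps lack-of-effect failures in PP. If days after discontinuation count as missed, every such failure with a last dose on Day 10 or earlier leaves PP through the consecutive-days rule. The same subject is also labelled non-compliant by the 14-dose floor. This covers any failure stopped at Visit 4.

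Its effect on the equivalence estimate cannot be calculated, because the documents give no expected number of early failures by arm. The illustration shows that an imbalance between arms matters and equal numbers hardly do. Whether the exclusion would take place cannot be settled from the redacted PP definition.

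The effect of the fixed 17 doses and 16 days on adherent subjects is real but descriptive only: 88% or 94%, with 2 or 1 missed doses charged.

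The results assume one dose a day with two on Day 0, the visit-day dose taken before the visit, no dosing after Visit 5, and no misses before the last dose. The wording should be settled before PP membership is determined.

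**What to change.** **Main change, SAP 7.8.9 and 6.3.** State that, for PP membership, missed doses, consecutive missed days and the 14-dose minimum are judged only over the period up to discontinuation. State also that neither the consecutive-days rule nor the 14-dose minimum removes from PP a subject whom the Synopsis classes as a treatment failure. The second sentence is essential, because 14 doses cannot be reached before Day 11 on this schedule. Carry the same exception into the Protocol Deviations List, since programmed deviations take precedence.

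**Reconcile** the Synopsis (Test of Equivalence), Protocol 9.0, Protocol 11.7 and SAP 7.8.9 on three matters: who among worsening subjects is in PP, whether the limit is 3 or more than 3 consecutive misses, and how the 14-dose minimum fits a Visit 5 window that allows 1 miss on Day 12 and 3 on Day 14. The dosing end date in the schedule and the dose before a late Visit 5 in Appendix II also need to agree. Record any resulting departure from the protocol in SAP 8.

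**Secondary, descriptive.** End each subject's planned-dose count and missed-dose window at the earliest of Day 14, Visit 5 or discontinuation.

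**Cost.** Wording in the SAP and the deviations list, a clarification of the protocol sections, one derived end-of-dosing-period date and one flag for lack-of-effect discontinuation. No new data collection is needed, since the discontinuation date and reason are already recorded under Protocol 9.0.

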7.8.10 Exposure to Concomitant Medication

Medication or non-drug therapy will be classified as prior, if the end date is known and is prior to the first use of the study drug. Medications and non-drug therapies that are ongoing or ended after the first use of the study drug will be classified as concomitant. If the end date of the medication or non-drug therapy is unknown, it will also be considered concomitant.

The concomitant medications will be summarized by preferred term for each treatment group as coded by the World Health Organization Drug (WHODRUG) dictionary Sept-2017 and be listed in a by-subject listing. Prior medications will be listed only.

7.8.11 Other assessments

Details of contraception method used by the subjects will be listed.

Urine pregnancy test will be performed for females of childbearing potential at Visit 1 Screening, Visit 2 Day 0 and Visit 5 Day 14. Results will be listed.

Details of the study drug and diary accountability will be listed.

General comments collected on the eCRF will be listed.

8. CHANGES FROM PROTOCOL-SPECIFIED ANALYSES

There are no changes from the protocol-specified analyses.

9. LIST OF PLANNED TABLES, FIGURES, AND LISTINGS

See separate document with the table, figure and listing shells.

10. LITERATURE CITATIONS / REFERENCES

1. Study Protocol: "A randomized, multicenter, double masked, placebo controlled, parallel group, bioequivalence study to evaluate the clinical equivalence and safety of Nepafenac 0.3% ophthalmic suspension ([REDACTED] Actavis LLC) with Ilevro™ (Nepafenac ophthalmic suspension), 0.3% of Alcon Laboratories, Inc. for the treatment of pain and inflammation associated with cataract surgery", version 2.0 dated Feb 22, 2018.

11. APPENDICES**11.1 Study visit Schedule**

Visit Details	Visit 1	Telephone Call	Visit 2	Visit 3	Visit 4	Visit 5
Study Activities	Day -7 to -1 Screening/ Baseline/ Randomization	Day -1 Pre-Operative Telephone Call	Day 0 The Day of Cataract Surgery	Day 1 One Day After Cataract Surgery	Day 7 \pm 2 days Follow-up visit	Day 14 \pm 2 days (End of Study / Early Discontinuation)
Informed Consent Process	×					
Medical History & Demographics	×					
Pre-Operative Call		×				
Physical Examination	×					×
Vital Signs	×		×	×	×	×
Inclusion/Exclusion Review	×					
Schedule the day for Cataract Surgery	×					
Assessment of Ocular Pain	×			×	×	×
Visual Acuity	×				×	×
Slit Lamp Examination	×			×	×	×
Intraocular Pressure	×			×	×	×
Fundus Examination	×					×

Laboratory Assessments (hematology, biochemistry and urine analysis)	×					×
Urine Pregnancy Test	×		×			×
Dispense/Administer Study drug	×		×	×	×	×
Dispense Subject Diary	×			×	×	
Retrieval/Review of Subject Diary					×	×
Retrieval of Study Medication						×
Concomitant Medication Assessment	×		×	×	×	×
Adverse Event Assessment	×	×	×	×	×	×

11.2 Aqueous Cells Scale

Grade	Aqueous Cells: Determined using a narrow slit beam (0.5 mm width at least 8mm length) at maximum luminance. Pigment and red blood cells are to be
0	None
1	1 to 5 cells
2	6 to 15 cells
3	16 to 30 cells
4	Greater than 30 cells

11.3 Aqueous Flare Scale

Grade	Aqueous Flare: Determined using a narrow slit beam (0.5 mm width at least 8mm length) at maximum luminance.
0	No visible flare when compared with the normal eye.

1	Mild-Flare visible against dark pupillary background but not visible against iris background.
2	Moderate-Flare is visible with the slit-lamp beam aimed onto the iris surface as well as the dark pupillary background.
3	Severe-Very dense flare. May also present as a “hazy” appearance of anterior segment structures when viewed with low power magnification of the slit-lamp. Present as pronounced Tyndall effect.

11.4 Ocular Pain Scale

Grade	Ocular Pain: A positive sensation of the eye, including foreign body sensation, stabbing, throbbing or aching.
0	None- absence of positive sensation
1	Patient reports presence of mild sensation or discomfort typical of post-operative ocular surgery, e.g., diffuse or focal foreign body sensation, mild transient burning or stinging.
2	Mild- mild, tolerable aching of the eye.
3	Moderate- moderate or more prolonged aching sufficient to require the use of over-the-counter analgesics (e.g. acetaminophen).
4	Moderately Severe- More prolonged aching requiring the use of any over-the-counter analgesics other than acetaminophen.
5	Severe- Patient reports intense ocular, periocular, or radiating pain (e.g., constant or nearly constant sharp stabbing pain, throbbing or aching, etc.) requiring prescription analgesics.

11.5 Code Fragments

Superiority analysis

```
proc freq data=<dataset>
  tables <treatment>*<cure> / fisher;
run;
```

Note: this analysis needs to be performed separately for test and reference treatments on a dataset containing only test and placebo or reference and placebo treatment subjects.

Clinical equivalence analysis

```
proc freq data=<dataset>  
  tables <treatment>*<cure > / riskdiffc;  
run;
```

Note: this analysis needs to be performed on a dataset containing test and reference treatment subjects only.

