#### **12.9 Test of Bioequivalence**

For the primary efficacy parameter, i.e. the proportion of patient(s) in the per protocol population identified as "treatment success" occurring at Visit 5 (end of the study on day  $14 \pm 2$  days)., a two-sided 90% confidence interval for the difference in success proportions  $(P_T - P_R)$  between test and reference products should be contained within [-0.20, +0.20] in order to establish equivalence.

The above analyses of therapeutic equivalence will be performed for the per-protocol population.

The detailed description of the statistical analysis to be used for the statistical evaluation & construction of 90% confidence interval will be elaborated in the Statistical Analysis Plan (SAP).

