5. HYPOTHESES TESTING

Hypothesis of Equivalence

A two-sided, continuity-corrected, 90% confidence interval on the Test-to-Reference difference for the proportion of subjects with cure will be constructed.

Bioequivalence will be established if the 90% confidence interval for the difference is contained within the interval [-0.20, +0.20].

Hypothesis of Superiority

The null hypothesis to be tested is that there is no difference in the proportions of subjects with cure. The evaluation of superiority will be conducted separately for the Test treatment versus the Placebo treatment and for the Reference treatment versus the Placebo treatment. The analysis will be conducted using two-sided, $\alpha = 0.05$, Fisher's exact test.

Superiority will be established if the proportion of cure for each active treatment is greater than, and statistically different from, that of the Placebo.

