7. STATISTICAL METHODS OF ANALYSIS

7.1 General Principles

The statistical analyses will be performed by [REDACTED] under the direction of the Sponsor, Actavis LLC, using SAS Version 9.4 (or higher). All tables, figures, and listings will be produced in the landscape format.

In general, all data will be listed by treatment group, subject and visit/time point where appropriate. The summary tables will also be stratified by, or have columns corresponding to, treatment groups.

All subjects will be identified by their unique subject numbers.

The total number of subjects in the study group (N) under the stated population will be displayed in the header of summary tables.

Data will be summarized using descriptive statistics for continuous variables. Unless otherwise specified, descriptive statistics will include number of subjects, mean, standard deviation, minimum, median, and maximum. The minimum and maximum statistics will be presented to the same number of decimal places as the original data. The mean and median will be presented to one more decimal place than the original data. The standard deviation will be presented to two more decimal places than the original data. The number of missing observations will be presented only if non-zero.

In summary tables of categorical variables, counts, and percentages will be used. The count [n] indicates the actual number of subjects in a particular category, which should always be less than or equal to the total number of subjects in the respective study group with known (non-missing) category [M]. Percentage will be obtained by: $\% = n/M * 100$. Unless otherwise stated, all percentages will be expressed to one decimal place.

All statistical tests will be two-sided at a significance level of $\alpha = 0.05$, unless otherwise indicated. No adjustment will be made for multiplicity.

The eye on which the cataract surgery is performed will be referred to as the study eye, and the other eye as the non-study eye. Ocular safety information will be presented separately for the study eye and non-study eye. Efficacy will be assessed for the study eye only.

Baseline will be defined as the last assessment obtained prior to the first dose of the study drug, unless otherwise specified.

Relative days will be calculated relative to date of first dose of study medication. Relative days will be calculated as follows only when the full assessment date is known (i.e., partial dates will have missing relative days).

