7.7.1.1 Analysis of clinical equivalence of test and reference treatments

A two-sided, continuity-corrected, 90% confidence interval on the Test-to-Reference difference for the proportion of subjects with cure will be constructed. Bioequivalence will be established if the 90% confidence interval for the difference is contained within the interval [-0.20, +0.20] for the PP population.

Analysis of bioequivalence will be performed on the PP population.

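### The equivalence code in SAP 11.5 sets no confidence level, so at the SAS default it returns 95% limits instead of the 90% limits the decision rule requires

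*SAP*

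**What the plan says.** The decision rule is the same wherever it is stated. Protocol 12.9 asks for "a two-sided 90% confidence interval for the difference in success proportions" between test and reference, to be contained in [-0.20, +0.20]; the synopsis gives the same level and margin. SAP 7.7.1.1 adds the continuity correction: "A two-sided, continuity-corrected, 90% confidence interval on the Test-to-Reference difference for the proportion of subjects with cure will be constructed". SAP 5 repeats the criterion: "Bioequivalence will be established if the 90% confidence interval for the difference is contained within the interval" [-0.20, +0.20]. SAP 7.7.1.1 ties it to the per-protocol (PP) population.

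The code for this analysis is in SAP 11.5, under the clinical equivalence label: "tables <treatment>*<cure > / riskdiffc". Its only accompanying note restricts the dataset to test and reference subjects. The superiority fragment beside it, "tables <treatment>*<cure> / fisher", also sets no level, but that analysis is planned at 0.05 and needs none.

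SAP 7.1 names SAS 9.4 or higher and sets the general level: "All statistical tests will be two-sided at a significance level of" 0.05, unless otherwise indicated. SAP 8 states: "There are no changes from the protocol-specified analyses".

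**The concern.** The code line carries over one of the two features that SAP 7.7.1.1 specifies for the interval, the continuity correction, and omits the other, the 90% level. `RISKDIFFC` applies the correction and leaves the level unchanged. With no `ALPHA=` option, PROC FREQ uses 0.05 and prints 95% limits.

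This is the primary analysis of a bioequivalence study. If the printed limits were compared with ±0.20 as they stand, the trial would be judged by a stricter rule than the one it prespecified, and the main objective could fail on a result that meets that rule. If the mismatch came to light after unmasking, on a borderline result, moving from 95% to 90% limits would look like a post hoc change even though the text supports it.

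**Working it through.** **Level required and level produced**

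| Source | Two-sided level | Multiplier z |
|---|---|---|
| Protocol 12.9, SAP 5, SAP 7.7.1.1 | 90% (alpha 0.10) | 1.645 |
| SAP 11.5 code at the PROC FREQ default | 95% (alpha 0.05) | 1.960 |

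The sampling-error part of the interval is 1.960/1.645 = 1.19 times as wide. PROC FREQ also has an equivalence sub-option that prints 100(1 - 2·alpha)% limits, which would be 90% at the default, but the fragment does not request it.

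**Formula.** With n per arm, the continuity-corrected Wald limits are

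d ± [ z·√(pT(1-pT)/n + pR(1-pR)/n) + ½(1/n + 1/n) ], where d = pT - pR.

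**Inputs that must be assumed.** The total is about 450 in three arms (SAP 3.1 and 3.2). The allocation, the planning rates and most PP criteria are redacted, so the arm sizes are assumptions: 150 per active arm (1:1:1) or 180 (2:2:1), with no PP loss. For the cure rate I use a proxy, Day 14 inflammation resolution in the two label studies (Protocol Appendix III, label section 14): (552 + 331)/(851 + 540) = 883/1391 = 63.5%. That is resolution of cells and flare in all randomized subjects, not this trial's composite cure in the PP population, so 80% is shown as an alternative.

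**Worked example, 150 per arm: 81/150 test, 95/150 reference**

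- d = 0.5400 - 0.6333 = -0.0933
- Standard error = √(0.5400×0.4600/150 + 0.6333×0.3667/150) = 0.0566
- Continuity correction = 1/150 = 0.0067
- 90%: half-width 1.645×0.0566 + 0.0067 = 0.0998, limits -0.193 to +0.006, inside ±0.20
- 95%: half-width 1.960×0.0566 + 0.0067 = 0.1176, limits -0.211 to +0.024, outside

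At 180 per arm, 96/180 versus 114/180 also splits: d = -0.100, 90% limits -0.191 to -0.009 (pass), 95% limits -0.207 to +0.007 (fail).

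**Probability of declaring equivalence.** Each figure is the exact sum, over two independent binomials, of the probability that both limits lie within ±0.20.

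| True cure, test vs reference | 150/arm, 90% limits | 150/arm, 95% limits | 180/arm, 90% limits | 180/arm, 95% limits |
|---|---|---|---|---|
| 63.5% vs 63.5% | 93.7% | 87.1% | 97.2% | 94.1% |
| 58.5% vs 63.5% | 82.0% | 71.6% | 87.7% | 80.0% |
| 80% vs 80% | 98.9% | 97.4% | 99.7% | 99.2% |
| 75% vs 80% | 90.8% | 84.5% | 95.0% | 90.8% |
| 43.5% vs 63.5% (at the margin) | 3.5% | 2.0% | 3.8% | 1.8% |

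The last row is the false-equivalence risk. It falls under 95% limits, so the error is conservative.

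**Effect of PP loss.** If 20% of 150 were excluded (150×0.8 = 120 per arm), then with no true difference and cure between 61% and 65%, power would be 83.8% to 85.9% with 90% limits and 73.3% to 75.4% with 95% limits.

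**The case against.** The strongest reply is that the fragment is silent and does not contradict the rule. It states no level, the SAP text states 90% without ambiguity, and nothing in either document plans a 95% interval for this comparison. The code is a sketch with placeholders for the dataset and variables, and it lacks a semicolon after the PROC statement (possibly a conversion artefact), so a programmer must complete it anyway with SAP 7.7.1.1 at hand. The 0.05 in SAP 7.1 is qualified by its own exception clause, which the equivalence text meets. The table shells are in a separate document (SAP 9) and may already carry the 90% label. The software default is not in the documents. The harm is one-directional and could be undone by recomputing under the stated rule.

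Much of this stands. The decision rule is clear, SAP 7.1 does not conflict with it, the shells cannot be judged from here, and the harm arises only if the default output is used for the decision. It does not remove the point. Dataset and variable names are what one expects to fill in; the TABLES options are what such a fragment exists to fix in advance. This one fixes the correction and leaves the level to a default that differs from the text. Nothing else in the code, or in its note, supplies the level.

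**Conclusion.** The concern holds. Run as printed at the software default, the code for the primary equivalence analysis gives 95% limits where the protocol and SAP require 90%. The decision rule itself is sound and clearly stated; the fault is confined to the code line.

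The cost, if the output were used unchanged, is lost power and a possible false failure. At the assumed 150 to 180 per active arm with no PP loss and no true difference, power falls by 3.1 to 6.6 percentage points at 63.5% cure and by 0.5 to 1.5 points at 80% cure. With a true 5-point deficit it falls by 7.7 to 10.4 points (58.5% vs 63.5%) or 4.2 to 6.3 points (75% vs 80%). These sizes rest on assumed arm sizes and cure rates. The mismatch in level does not; it rests only on the printed code and the PROC FREQ default. It should be fixed before the analysis, but it does not threaten the validity of a positive conclusion.

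**What to change.** In SAP 11.5, change the equivalence statement to `tables <treatment>*<cure> / riskdiffc alpha=0.10;` before database lock. Confirm that the program output and the corresponding table shell are labelled as 90% limits. The superiority fragment needs no change on this account.

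The cost is one option in one line of the SAP. The design, the data collected and the stated decision rule are unaffected.
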